 Pruritus NRS, emollient use, time of study products administration, and fasting conditions will be recorded daily for 12 weeks in a subject diary. Pruritus NRS and emollient use will be recorded daily in a diary up to Week 16 visit for subjects not entering in the OLE study. Compliance to diary entry, including emollient use, will be verified by the site at every visit.

 Optional, only for a subset of approximately 68 subjects who consent. Photographs should be performed prior to drug administration and biopsy collection (for subjects consenting to biopsies).

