2 STUDY OBJECTIVES AND ENDPOINTS

OBJECTIVES	ENDPOINTS
Primary	Efficacy endpoint:
To evaluate the efficacy of ASN002 in subjects with moderate to severe atopic dermatitis (AD)	
 • Change from baseline in Eczema Area and Severity Index (EASI) score at Week 12
Secondary	
Efficacy endpoints:
 
 • Change from baseline in EASI score at Weeks 2, 4, and 8 • Percent change from baseline in EASI score at Weeks 2, 4, 8, and 12 • Proportion of subjects with at least a 50% reduction from baseline in EASI (EASI50) at Weeks 2, 4, 8, and 12 • Proportion of subjects achieving at least a 75% reduction from baseline in EASI (EASI75) at Weeks 2, 4, 8, and 12 • Proportion of subjects achieving at least a 90% reduction from baseline in EASI (EASI90) at Weeks 2, 4, 8, and 12 • Time to achieve EASI50, EASI75, and EASI90 relative to baseline.

	STATISTICAL ANALYSIS PLAN, Version Final 2.0
Protocol Number: ASN002AD-201 V3.0	Sponsor: Asana BioSciences, LLC

OBJECTIVES	ENDPOINTS
	
 • Proportion of subjects achieving at least a 2-grade reduction from baseline to clear (0) or almost clear (1) in Investigator's Global Assessment (IGA) at Weeks 2, 4, 8, and 12 • Proportion of subjects achieving at least a 2-grade reduction from baseline in IGA at Weeks 2, 4, 8, and 12 • Change and percent change from baseline in SCORing Atopic Dermatitis (SCORAD) (total score, sleep score, pruritus score) at Weeks 2, 4, 8, and 12 • Change from baseline in 5-D Pruritus Scale at Weeks 2, 4, 8, and 12 • Change and percent change from baseline in single daily timepoint pruritus Numeric Rating Scale (NRS) at Week 1 (Day 2 up to Day 7) • Change and percent change from baseline in weekly average of the peak daily pruritus NRS at Weeks 1, 2, 4, 8, and 12 • Proportion of subjects achieving at least a 4-point reduction from baseline in weekly average of the peak daily pruritus NRS at Weeks 1, 2, 4, 8, and 12 • Time to achieve at least 4-point reduction from baseline in NRS. • Change and percent change from baseline in Body Surface Area (BSA) involved with AD at Weeks 2, 4, 8, and 12 • Change from baseline in Patient Oriented Eczema Measure (POEM) at Weeks 2, 4, 8, and 12 • Change from baseline in Dermatology Life Quality Index (DLQI) at Weeks 2, 4, 8, and 12
	Safety endpoints:

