6.6 Examination of Subgroups

The effect of EASI score at baseline (disease severity) on the treatment effect will be examined for the change-from-baseline EASI, %change-from-baseline EASI, and % subjects with at least a 50%, 75% and 90% reduction in EASI, % subjects achieving at least a 2-grade reduction from baseline to clear (0) or almost clear (1) in IGA, % subjects achieving at least a 2-grade reduction from baseline in IGA.

The change and percent change from baseline in single daily timepoint pruritus NRS at Week 1 (Day 2 up to Day 7) and the change and percent change from baseline in weekly average of the peak daily pruritus NRS at Weeks 1, 2, 4, 8, and 12 as well as the % subjects achieving at least a 4-point reduction from baseline in weekly average of the peak daily pruritus NRS at Weeks 1, 2, 4, 8, and 12 will be presented in the subgroup of subjects with baseline NRS ≥ 4 .

Moreover, inferential statistical analysis will be done at Week 12 for change-from-baseline and %change-from-baseline EASI. Details on the inferential statistical analysis are presented under section 12.1 Primary Efficacy Endpoint.

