Subjective items include loss of sleep and the intensity of pruritus. These are evaluated by having the subjects indicate on a 10.0-cm (0.0 – 10.0) visual analog scale (VAS) the point corresponding to the average value for the last 3 days/nights. The combined maximum score of these two is 20.0.

The sum of the measures above represents the SCORAD, which can vary from 0 to 103. If the subjective scores of pruritus and loss of sleep are excluded, the SCORAD becomes objective SCORAD (score range 0.0-83.0). The score will be set to missing in case of at least one missing value.

SCORAD will be assessed as

[figure not shown]
	STATISTICAL ANALYSIS PLAN, Version Final 2.0
Protocol Number: ASN002AD-201 V3.0	Sponsor: Asana BioSciences, LLC

- the change from baseline in total SCORAD score, sleep and pruritus sub-scores at Weeks 2, 4, 8, and 12.
- The percent change from baseline in total SCORAD score, sleep and pruritus sub-scores at Weeks 2, 4, 8, and 12.

Pruritus Numeric Rating Scale (NRS):

The intensity of pruritus will be recorded for the entire duration of the treatment (daily) using a numeric rating scale (NRS). This will be evaluated by asking subjects to assign a numerical score representing the worst intensity over the last 24 hours of their symptoms on a scale from 0 to 10, with 0 indicating no symptoms and 10 indicating the worst imaginable symptoms. The pruritus NRS is presented in Figure 2. Assessments within 7 days prior to each of the Week 2, 4, 8, and 12 visits, and on Days 2 to 7 of the Week 1 visit, will be used for the calculation of the weekly average of pruritus NRS.

Figure 2: Pruritus Numeric Rating Scale

The pruritus numeric rating scale will be assessed as:

- Change and percent change from baseline in single daily timepoint NRS at Week 1 (i.e. Day 2, Day 3, up to Day 7).
- Change and percent change from baseline in weekly average of the peak daily pruritus NRS at Weeks 1, 2, 4, 8, and 12.
- Proportion of subjects achieving at least a 4-point reduction from baseline in weekly average of the peak daily pruritus NRS at Weeks 1, 2, 4, 8, and 12.

	STATISTICAL ANALYSIS PLAN, Version Final 2.0
Protocol Number: ASN002AD-201 V3.0	Sponsor: Asana BioSciences, LLC

- Time to a 4-point reduction from baseline in weekly average of the peak daily pruritus NRS.

5D-Pruritus Scale:

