Additional exploratory analyses may be performed to further understand the impact, if the results of the sensitivity analyses excluding the subjects for whom the IGA form was initially used to capture the vIGA assessment at baseline reveal inconsistencies with the results including those subjects.

The time to achieve the 50%, 75%, or 90% reduction in EASI relative to baseline and the time to achieve a 4-point reduction from baseline in weekly average of the peak daily pruritus NRS will be compared between treatments using the Kaplan Meier method. A subject will be considered as censored if he has not met the event of interest at the end of the study (Week 12 visit) or if the subject is lost to follow up at last observation. Those subjects will be censored at their last available EASI (or NRS) assessment.

Information for stratification factors will be taken from the EDC database, and not the IWRS for all secondary endpoint analyses.

Descriptive statistics will be presented on all secondary endpoints by visit and treatment group.

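### Time to a 4-point itch reduction is read from five weekly averages although the diary is daily, and SAP 6.6 omits this endpoint from the baseline NRS ≥4 analyses

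*SAP*

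**What the plan says.** **Data collected.** Footnote 14 to the protocol's Table 1 states: "Pruritus NRS, emollient use, time of study products administration, and fasting conditions will be recorded daily for 12 weeks in a subject diary". SAP 12.2 agrees: "The intensity of pruritus will be recorded for the entire duration of the treatment (daily) using a numeric rating scale (NRS". Each entry is the worst itch of the past 24 hours, scored 0 to 10.

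**Weekly average.** SAP 12.2 names the entries that feed it: "Assessments within 7 days prior to each of the Week 2, 4, 8, and 12 visits, and on Days 2 to 7" for Week 1. No average is defined for any other week.

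**Time endpoint.** SAP 12.2 lists "Time to a 4-point reduction from baseline in weekly average of the peak daily pruritus NRS". Under Secondary Endpoint Analyses it says the "reduction from baseline in weekly average of the peak daily pruritus NRS will be compared between treatments using the Kaplan Meier method". Subjects without the event are censored at their last available NRS assessment. SAP section 2 words the same endpoint without a weekly average: "Time to achieve at least 4-point reduction from baseline in NRS". The endpoint is absent from the list in protocol section 3, and SAP 3.5 does not record it as a change, so the SAP is its only definition.

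**Who is analysed.** SAP 12.2 assigns secondary parameters to the mITT population. Eligibility (protocol 5.1) sets minima for EASI, IGA and BSA but none for the NRS. SAP 6.6 says that change, percent change and the 4-point proportion "will be presented in the subgroup of subjects with baseline NRS" of at least 4. Time to a 4-point reduction is not on that list.

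**The concern.** A time-to-response endpoint exists to say when relief begins. EASI is scored only at visits, so time to EASI50 has to be coarse. The itch diary is daily, yet the stated rule puts the NRS time endpoint on nearly the same visit grid. Under that rule a Kaplan-Meier median can only fall at Week 1, 2, 4, 8 or 12, and after Week 4 the looks are four weeks apart.

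The second issue is the risk set. A subject whose baseline NRS is 0 to 3 cannot fall by 4 points and can only be censored. The SAP deals with this for the 4-point proportion through the 6.6 subgroup, but not for the matching time analysis. At stake are the reported onset times, the medians and the height of the curves.

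**Working it through.** The documents give no power, event count or hazard ratio for this endpoint, so there is no planned figure to reproduce.

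**1. Diary days used.** Inputs: the five windows in SAP 12.2, visits on the target days in SAP 5.4 (14, 28, 56, 84), and post-baseline diary Days 2–84.

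- Used: 6 (Days 2–7) + 4 × 7 = 34 days of 83. If the 7 days before a Day 14 visit are read as Days 7–13, Day 7 is shared with Week 1 and the count is 33.
- Unused: 83 − 34 = 49 days, and 49/83 = 59%.
- Weeks with no average: 3, 5, 6, 7, 9, 10 and 11, which is 7 of 12.

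**2. Recording delay.** Each true first-response week is mapped to the next week with a defined average, assuming that the response lasts until then.

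| True week | 1 | 2 | 3 | 4 | 5 | 6 | 7 | 8 | 9 | 10 | 11 | 12 |
|---|---|---|---|---|---|---|---|---|---|---|---|---|
| Recorded | 1 | 2 | 4 | 4 | 8 | 8 | 8 | 8 | 12 | 12 | 12 | 12 |
| Delay (weeks) | 0 | 0 | 1 | 0 | 3 | 2 | 1 | 0 | 3 | 2 | 1 | 0 |

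The onset distribution is not in the documents, so the mean delay is given for a range of assumptions:

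- Uniform over 12 weeks: 13/12 = 1.08 weeks.
- Constant hazard, 30% to 70% responding by Week 12: 1.05 to 0.97 weeks, with 57% to 53% of responders dated late.
- Front-loaded (Weibull shape 0.6, 50% responding): 0.75 weeks, with 41% dated late.
- Uniform over Weeks 1–4 only: 1/4 = 0.25 weeks.

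**3. Responses that are missed.** SAP 6.2 sets efficacy data after the start of a prohibited medication to missing. Protocol 6.4.2 lets subjects who start a prohibited topical after the first 4 weeks continue study assessments. Take a first response in Week 5 (Days 29–35) and a prohibited topical begun on Day 45. The Week 8 window opens on about Day 49, so no usable average follows Week 4 and the response is not counted. A response lost again before the next window opens is missed in the same way.

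**4. Censoring.** Events are seen only in the five windows, but the last available NRS assessment is naturally read as a diary day. A subject without the event whose last entry is Day 48 would count as event-free to Day 48, although the last computed average was at Week 4 (Day 28).

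**5. Subjects who cannot respond.** Let f be the share with baseline NRS below 4 (not in the documents; 0–20% assumed) and p the Week 12 response among those able to respond (also assumed). The observed Week 12 response is (1 − f) × p.

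| f | p = 50% vs 25% | Difference (points) |
|---|---|---|
| 0 | 50 vs 25 | 25 |
| 5% | 47.5 vs 23.75 | 23.75 |
| 10% | 45 vs 22.5 | 22.5 |
| 20% | 40 vs 20 | 20 |

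Medians can disappear. With p = 60% in an active arm, f = 20% gives 0.8 × 60% = 48%, so the median is no longer reached.

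**6. Comparison between arms.** The SAP names Kaplan-Meier but no test, so a two-sided 5% log-rank test is assumed. Simulation: 55 per arm, 2,000 runs, constant hazard, 50% vs 25% by Week 12 among those able to respond, no dropout.

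| f | All subjects, 12 weeks | All subjects, 5 looks | Baseline NRS ≥4, 12 weeks |
|---|---|---|---|
| 0 | 77.8% | 77.6% | 77.8% |
| 10% | 73.1% | 73.0% | 75.6% |
| 20% | 64.1% | 63.8% | 67.6% |

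The coarse grid costs 0.3 point of power or less. Analysing only subjects who can respond recovers 2.5 to 3.5 points at f = 10% to 20%.

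**The case against.** The strongest reply is that onset is already covered where it matters most. The SAP analyses daily change in NRS on Days 2–7, and Weeks 1 and 2 each have an average. The protocol's background (2.1.2) reports substantial itch decreases after 4 weeks of treatment. Within Weeks 1–4 only Week 3 is uncovered, and its delay is one week. The grid is the same in every arm, and the log-rank result hardly moves. The share below NRS 4 may be close to zero in a population with EASI ≥16, IGA ≥3 and BSA ≥10%. The endpoint is secondary, with nominal p-values (SAP 6.5).

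All of that stands, and it limits the point to reported times, medians and curve height.

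A reader might also infer more than the documents support:

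- **That a missed visit removes a week of diary data.** The NRS rule is silent on missed visits, and SAP 5.4 supplies target days that could anchor the window.
- **That any response in Weeks 5–7 followed by prohibited medication before the Week 8 visit is lost.** Only data after the start are set to missing. If the start falls inside the 7-day window, the earlier entries remain, and no minimum number of days voids the average.
- **That subjects with baseline below 4 stay at risk for all 12 weeks.** They are censored at their last assessment, so this holds only for those with NRS data to Week 12.
- **That dilution could produce a false positive.** Randomization should balance f, so the effect is attenuation.

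**Conclusion.** The point holds in a limited form. As SAP 12.2 is written, a first 4-point response in Weeks 3, 5–7 or 9–11 is dated 1 to 3 weeks late. The mean is 0.75 to 1.1 weeks across the 12-week onset patterns assumed here, and less if onset is concentrated in the first four weeks. A response that ends, or is followed by prohibited medication, before the next window opens is missed. Onset in Weeks 1, 2, 4, 8 and 12 is not delayed.

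Subjects with baseline NRS below 4 cannot have the event and lower the curves by the factor 1 − f. The documents do not give f, and the effect is nil if there are none. SAP 6.6 covers such subjects for the 4-point proportion but not for the time endpoint.

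The primary conclusion is untouched and the test between arms is almost unchanged. The change is worth making because it is cheap, uses data already collected, and corrects the quantity that this endpoint reports.

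**What to change.** Before unblinding, amend the SAP as follows.

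1. **12.2, time endpoint only.** Compute a weekly average for each of Weeks 1 to 12 from the daily diary. Keep the Week 1, 2, 4, 8 and 12 averages identical to those behind the 4-point proportion, so that the two endpoints agree for any subject. Define the remaining weeks by study day (for example Days 15–21 for Week 3). Say how to treat a day shared by adjacent windows, since visits may move by 1 or 2 days. The event is the first week with a reduction of at least 4 points.
2. **12.2, censoring.** Censor subjects without the event at the last week with a computed average.
3. **6.6.** Add time to a 4-point reduction in subjects with baseline NRS ≥4, reported alongside the mITT analysis.
4. **Section 2.** Use the weekly-average wording of 12.2.

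Leave mITT as the analysis set for the 4-point proportion. That is a protocol endpoint, SAP 6.6 already presents the subgroup, and swapping the lead set would be a matter of preference.

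The cost is SAP wording and minor programming, with no new data. The baseline NRS ≥4 time analysis will have somewhat fewer subjects, by the unknown share f.

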3.4 Randomization, Replacement, and Unblinding Procedures

Approximately 220 subjects will be randomized in a 1:1:1:1 ratio to receive either ASN002 40 mg, 60 mg, or 80 mg, or placebo, in order to complete the study with 160 evaluable subjects.

Randomization will occur prior to first dosing, at Day 1 visit. The randomization list will be generated using a validated software. Randomization will be stratified by baseline disease severity at Day 1 ([EASI = 16.0-21.2] vs. [EASI = 21.3-29.9] vs. [EASI = \geq 30.0]) and biopsy collection. The master randomization list will be kept secured until the study blind is broken at the end of study. This list will be uploaded into an Interactive Web Response System (IWRS). The investigator or designee will be able to acquire a randomization number for eligible subjects by connecting to the IWRS.

This study will be double-blinded. At all times, treatment and randomization information will be kept confidential and will not be released to the investigator, the study staff, the contract research organization (CRO), or the sponsor's study team until after the conclusion of the study.

Safety oversight will be under the direction of an independent DSMB, who will remain unblinded during the study.

	STATISTICAL ANALYSIS PLAN, Version Final 2.0
Protocol Number: ASN002AD-201 V3.0	Sponsor: Asana BioSciences, LLC

Blinding codes should only be broken in emergency situations for reasons of subject safety. If unblinding the treatment assignment for a subject is necessary due to a medical emergency (an unexpected SAE per product's safety profile) and other significant medical situations such as pregnancy, the investigator can make the decision to unblind the treatment assignment if knowing the treatment assignment will help treatment decision of the particular AE. When the blind for a subject has been broken, the reason must be fully documented in the source document and eCRF. Whenever possible, the investigator should contact the sponsor or its designee before breaking the blind. If the blind is broken, the investigator should promptly inform the medical monitor. Documentation of breaking the blind should be recorded with the date/time and reason why the blind was broken, and the names of the personnel involved.

The subject for whom the blind has been broken will be discontinued from the study and undergo the ET procedures.

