3.5 Changes to the Analysis from the Protocol

Section 8.3.2 of the protocol mentions the inclusion of stratification factors as fixed effects in the statistical model. The biopsy collection stratification factor was included for an operational purpose only (to have samples for biopsy in the four treatment groups), therefore this variable was not included in any of the statistical models. In addition, for the primary endpoint EASI, the baseline value will not be included as covariate in the statistical model, since it is already included as stratification factor (baseline disease severity) and to include both variables would create a problem of multicollinearity.

In section 8.3.2 of the protocol, Bonferroni adjustment was proposed to adjust for the multiple dose comparisons between ASN002 and placebo. It is well known that the Bonferroni adjustment is overly conservative. Therefore, Hochberg adjustment will be used for the multiple dose comparisons. The decision for this change was made before the unblinding. Since this change would not affect the conduct of the trial in any sense, no protocol amendment was made to account for this change.

The section 8.3.3 of the protocol has planned for summary of physical exams using descriptive statistics presenting the value at each visit as well as the change from baseline. Since significantly

	STATISTICAL ANALYSIS PLAN, Version Final 2.0
Protocol Number: ASN002AD-201 V3.0	Sponsor: Asana BioSciences, LLC

abnormal physical exams will be presented in the summary of AEs, only listings of physical exams will be presented.

The following endpoints are listed in the protocol:

- 1) Proportion of subjects achieving at least a 2-grade reduction from baseline to clear (0) or almost clear (1) in Investigator's Global Assessment (IGA) at Weeks 2, 4, 8, and 12
- 2) Proportion of subjects achieving an IGA of clear (0) or almost clear (1) at Weeks 2, 4, 8, and 12

Since the study has an inclusion criterion of 3 and 4 on IGA, both endpoints will contain exactly the same set of subjects. For this reason, only the first endpoint listed above will be provided.

Data from site 027 has been deemed unreliable. For this reason, all data from this site will be excluded from all analysis for this study (both safety and efficacy).

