5.1 Sample Size

Using the following assumptions for the primary efficacy endpoint: a change-from-baseline in EASI at week 12 of at least -15 in the ASN002 dosing groups, a change-from-baseline of -8 in the placebo group, a common standard-deviation of 8, nominal alpha of 0.0167 for each comparison of interest, we would need 40 evaluable subjects per group in order to achieve a power of 92% on the primary efficacy endpoint.

Moreover, with 46 subjects per group, we would have 80% power to show a statistically significant difference between the higher dosing group and placebo in IGA responses (one of the key secondary efficacy endpoint), assuming a response of 37.5% vs. 11.1% in the higher dosing and placebo groups, respectively, using an alpha of 5%.

Thus, assuming about 15% dropout rate, 55 subjects per group will need to be enrolled in this trial for a total of 220 subjects in order to have a minimum of 46 subjects per group to evaluate efficacy with adequate power.

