6 STATISTICAL CONSIDERATIONS

6.1 Adjustments for Covariates

Baseline value for the absolute change from baseline of continuous efficacy parameters will be included as covariate in the statistical models.

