1. If one question is left unanswered this is scored 0 and the scores are summed and expressed as usual out of a maximum of 30.
2. If two or more questions are left unanswered the questionnaire is not scored.
3. If question 7 is answered 'yes' this is scored 3 even if in the same question one of the other boxes is ticked.
4. If question 7 is answered 'no' or 'not relevant' but then either 'a lot' or 'a little' is ticked this is then scored 2 or 1. If it is answered 'no', but the second half is left incomplete, the score will remain 0.

DLQI will be assessed as

- the change from baseline in DLQI at Weeks 2, 4, 8, and 12.

Secondary Endpoint Analyses

The same methods (MMRM and ANOVA) as described for the primary efficacy analyses (Section 12.1) will be performed to analyze the change and percent change in EASI.

Similar methods (MMRM and ANCOVA) as described for the primary efficacy analyses (Section 12.1) will be performed to analyze the change and percent change in NRS, SCORAD (MMRM and ANCOVA for total score; MMRM only for sleep and pruritus sub-scores) and BSA, and the change in 5D-Pruritus Scale (change from baseline only), POEM (change from baseline only) and DLQI (change from baseline only), with the addition of the baseline score as covariate in the models. Analyses will be based on the mITT population for all secondary parameters.

For categorical efficacy endpoints involving proportions of IGA, EASI and NRS (e.g. the proportion of subjects achieving at least a 2-grade reduction from baseline to clear (0) or almost clear (1) in Investigator's Global Assessment (IGA) at week 12), a Cochran Mantel Hansel test (CMH) controlling for the stratification variable (baseline disease severity) will be performed. For subgroup analyses at each level of baseline severity, a Chi-squared test will be performed. Analyses will be based on the mITT population for all secondary parameters and also on PP population for IGA.

	STATISTICAL ANALYSIS PLAN, Version Final 2.0
Protocol Number: ASN002AD-201 V3.0	Sponsor: Asana BioSciences, LLC

As a sensitivity analysis for IGA, the Cochran Mantel Hansel test (CMH) controlling for the stratification variable (baseline disease severity) will be performed, excluding the subjects for whom the IGA form was initially used to capture the vIGA assessment at baseline. This sensitivity analysis will be performed on the mITT and PP populations.

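### The NRS 4-point and IGA responder tests adjust for EASI severity only; a model with baseline NRS would sharpen the NRS response comparison at little cost

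*SAP*

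**What the plan says.** For the responder proportions on IGA, EASI and NRS, SAP 12.2 plans one method: "a Cochran Mantel Hansel test (CMH) controlling for the stratification variable (baseline disease severity) will be performed". No logistic model is planned.

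Own-scale baseline is used elsewhere. SAP 6.1 states: "Baseline value for the absolute change from baseline of continuous efficacy parameters will be included as covariate in the statistical models". SAP 12.2 then analyses change in NRS, SCORAD, BSA, 5-D pruritus, POEM and DLQI "with the addition of the baseline score as covariate in the models". Neither statement reaches the responder endpoints.

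Three other passages bear on the point:

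- **Randomisation.** SAP 3.4: "Randomization will be stratified by baseline disease severity at Day 1", in three EASI bands, and also by biopsy collection. Baseline IGA and NRS are not strata.
- **Role of IGA response.** SAP 5.1 says that with 46 per group "we would have 80% power to show a statistically significant difference between the higher dosing group and placebo in IGA responses", assuming 37.5% against 11.1% at alpha 5%. It calls IGA response a key secondary endpoint.
- **NRS subgroup.** Under SAP 6.6 the NRS results, including the 4-point response, "will be presented in the subgroup of subjects with baseline NRS" of at least 4. No adjusted test is attached to that presentation.

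SAP 6.5 leaves secondary p-values nominal.

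**The concern.** Whether a subject can respond depends on where that subject starts on the same scale.

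- **NRS.** The endpoint is "Proportion of subjects achieving at least a 4-point reduction from baseline in weekly average of the peak daily pruritus NRS". The inclusion criteria set no minimum NRS, so subjects below 4 can enter. They cannot respond, yet they stay in the main comparison.
- **IGA.** SAP 3.5 reasons: "Since the study has an inclusion criterion of 3 and 4 on IGA". Reaching 0 or 1 therefore takes two grades from a baseline of 3 and three from a baseline of 4. For the plain 2-grade reduction the order may reverse, because 4 to 2 counts and 3 to 2 does not.

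For EASI50, EASI75 and EASI90 the EASI bands are themselves an own-scale baseline. IGA and NRS response are adjusted only for another scale's baseline, and the SAP gives no reason. At stake are some precision on NRS response and the reading of any dose-placebo comparison in which baseline NRS or IGA happens to be uneven. All three dose comparisons share one placebo arm, so an uneven placebo group would affect all of them.

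**Working it through.** **1. The plan's own figure.** Inputs from SAP 5.1 and 5.6: 37.5% vs 11.1%, 46 per group, two-sided alpha 0.05.

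- Mean rate = (0.375 + 0.111)/2 = 0.243.
- Null SE = √(2 × 0.243 × 0.757/46) = 0.0894.
- Alternative SE = √(0.375 × 0.625/46 + 0.111 × 0.889/46) = 0.0851.
- Power = Φ[(0.264 − 1.96 × 0.0894)/0.0851] = Φ(1.04) ≈ 85%.

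Exact enumeration of the uncorrected chi-square test gives 86.1%. Fisher's exact test and the continuity-corrected chi-square each give 80.0%, so the stated 80% reproduces. The planned CMH is closer to the uncorrected test and has about 5 points in reserve. Enrolment also reproduces: 46/0.85 = 54.1, rounded up to 55.

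**2. Validity.** In simulations at 46 per arm (40,000 trials per scenario), type I error of the EASI-only CMH was 4.8-5.4% throughout.

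**3. NRS response, CMH strata.** The documents give no NRS response rates or baseline distribution. Assumed here: 40% vs 15% response, none below baseline 4, and an odds ratio (OR) of response for baseline ≥7 vs 4 to <7.

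| Baseline <4 | OR | EASI only | NRS only | EASI × NRS |
|---|---|---|---|---|
| 10% | 1 | 78.7% | 79.9% | 78.6% |
| 10% | 5 | 78.3% | 83.6% | 82.5% |
| 20% | 1 | 78.1% | 81.3% | 79.9% |
| 20% | 5 | 78.4% | 86.2% | 84.9% |

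Other assumed scenarios, EASI only vs EASI × NRS:

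- Response 0/5/22% vs 0/20/58% for baseline <4, 4-6, 7-10 (15/35/50% of subjects): 75.5% vs 81.3%; repeated independently, 75.6% vs 80.5%.
- Same overall rates, flat response above 4: 74.2% vs 74.9%. Restricting to baseline ≥4 gives 76.6%.
- Flat, with only 5% below 4: 81.5% vs 80.8%.
- No dependence on baseline NRS: 75.8% vs 72.9%.

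Across methods and scenarios the change runs from about -3 to +8 points.

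**4. NRS response, logistic model.** In a separate set of simulations at 46 per arm with assumed distributions, treatment plus EASI stratum plus continuous baseline NRS gained about +0.5 to +6 points over the EASI-only CMH. Its type I error was 5.4-6.1%, so a small part of that gain reflects a slightly liberal test. In the same runs the 9-stratum CMH moved power by only -1 to +2 points. Its strata are thin: 92/9 ≈ 10 subjects each, about 5 per arm, and about 3 of 9 had fewer than 3 subjects in an arm.

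**5. IGA response, average power.** Assumed: about 40% with baseline IGA 4, OR of response for IGA 4 vs 3 from 1 to 0.1, and no to strong correlation with EASI. EASI-only power is 86-90%; EASI × IGA power is 85-91%. The change is about -1 at OR 1, 0 at OR 0.5, 0 to +1 at OR 0.33, 0 to +2 at OR 0.2, and +1 to +3 at OR 0.1.

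**6. IGA response, chance imbalance.** If IGA is unrelated to EASI, the SD of the between-arm difference in IGA 4 share is √(2 × 0.4 × 0.6/46) = 0.102, or 10 points; correlation with EASI shrinks it. In simulation the shares differ by more than 10 points in 16-34% of trials and by more than 20 points in 0-4%. With a fixed 20-point excess of IGA 4 on active and no correlation with EASI (worst case):

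| OR | Expected difference (26.4 if balanced) | Power, EASI only | Power, by IGA |
|---|---|---|---|
| 0.5 | 24.2 points | 79% | 85% |
| 0.33 | 23.1 points | 76% | 87% |
| 0.2 | 21.9 points | 72% | 88% |

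The opposite imbalance raises the expected difference to 28.6-30.8 points. Under the null, with a 20-point imbalance either way, type I error of the EASI-only CMH is 5.1-5.8%.

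**The case against.** The planned CMH stratifies on the severity factor used in randomisation and holds its level. Conditioning on an imbalance can make almost any omitted prognostic variable look harmful, and these endpoints carry nominal p-values only. SAP 6.6 already shows NRS response without the subjects who cannot respond, and NRS change is already adjusted for baseline. The larger NRS gains rest on an assumed steep gradient above 4 that appears nowhere in the documents; with a flat gradient, finer strata gain almost nothing or lose power. Stratifying on baseline IGA would also bring a doubtful measurement into the test, since SAP 12.2 plans a sensitivity analysis for subjects whose baseline vIGA was captured on the IGA form.

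Most of this stands. It rules out replacing the IGA test and rules out a 9-stratum NRS test. It does not answer the NRS point: a subgroup display does not adjust the mITT comparison, nor does it separate moderate from high baseline itch.

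A reader might infer that the plan loses power on IGA, the endpoint behind the 46 per group. The documents do not support that: they give no prognostic strength for baseline IGA, the average effect is near zero under most assumptions, and the 80% has reserve. A reader might also infer an inflated error rate. One simulation did give 8.0% for the EASI-only test, but only in trials where the IGA 4 share differed by at least 15 points (12% of trials) and under strong assumed dependence; moderate dependence gave 5.9%. Over all trials the error is about 5%.

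**Conclusion.** The point holds as a matter of precision and protection against chance imbalance, mainly for the NRS 4-point response. The SAP adjusts NRS change for baseline NRS but not NRS response, where subjects below 4 cannot count as responders. Adjustment is worth about -3 to +8 points of power across methods and scenarios, and about +0.5 to +6 points with a logistic model on continuous baseline NRS. For IGA response the average effect is about -1 to +3 points; a supportive analysis is justified by possible imbalance, not by lost power.

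All these sizes rest on assumptions absent from the documents: NRS response rates and baseline distribution, the IGA 4 share, its correlation with EASI, and the odds ratios. The planned test is neither biased nor invalid.

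**What to change.** Amend SAP 12.2 before unblinding:

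1. **NRS 4-point response.** Pre-specify a logistic regression with treatment, EASI stratum and continuous baseline NRS, report a standardised risk difference, and keep the EASI-only CMH alongside it. Do not use a CMH over nine EASI × NRS strata.
2. **Both IGA responder endpoints.** Leave the planned CMH in place. Add a supportive analysis with EASI stratum plus baseline IGA (3 vs 4), repeated without the subjects whose baseline vIGA was captured on the IGA form.

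The cost is SAP wording and minor programming, since both baselines are already collected and summarised (SAP 8). The downsides are a type I error slightly above 5% for the logistic test at this sample size, and up to about 1 point of power in the supportive IGA analysis if baseline IGA is not predictive. Timing matters: adding either baseline after an imbalance has been seen would look data-driven.
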